APPENDIX 5: INVESTIGATOR'S SIGNATURE	

List of Abbreviations

AE	Adverse Event
AUC	Area under the curve
BID	Bis in die (twice daily)
BPH	Benign prostatic hyperplasia
CFR	Code of Federal Regulations
CRF	Case Report Form
CRO	Contract Research Organization
CSME	Clinically significant macular edema
DHHS	Department of Health and Human Services
eCRF	Electronic Case Report Form
ETDRS	Early Treatment of Diabetic Retinopathy Study
FDA	Food and Drug Administration
GCP	Good Clinical Practice
HEC	Hydroxyethyl cellulose
HIPAA	Health Information Portability and Accountability Act
Hr	Hour
ICF	Informed Consent Form
ICH	International Conference on Harmonisation
IEC	Independent Ethics Committee
IND	Investigational New Drug Application
INF•	Interferon gamma
IOP	Intraocular Pressure
IRB	Institutional/Independent Review Board
ITT	Intent to Treat
LOCF	Last Observation Carried Forward
logMAR	Logarithm of the Minimum Angle of Resolution
mĹ	Milliliter
• g	Microgram
NCS	Not clinically significant
NDA	New Drug Application
NF-••	Nuclear factor kappa-light-chain-enhancer of activated B-cells
ng	Nanogram
NO	Nitric oxide
NQ01	NADH quinine oxidoreductase 1
Nrf2	Nuclear factor erythroid-derived 2
NSAID	Non-steroidal anti-inflammatory agent
PCIOL	Posterior chamber intraocular lens
PDR	Proliferative diabetic retinopathy
PHI	Protected Health Information
PP	Per Protocol
PVP	Polyvinyl pyrrolidone
QD	Quaque die (Once daily)

SAESerious Adverse EventSAPStatistical analysis planSUNStandardization of the Uveitis NomenclatureVAVisual acuity

1 INTRODUCTION

Following ophthalmic surgery, the current standard of care includes a topical ophthalmic corticosteroid or other anti-inflammatory agent to treat ocular inflammation and improve patient comfort. If left untreated, inflammation of the eye may result in further ocular complications including scarring, vision loss, or blindness. Although the exact dosing regimen is physician-dependent, patients are typically prescribed a topical corticosteroid for a period of 2-4 weeks following surgery, being tapered over the course of delivery as the inflammation subsides. Topical anti-inflammatory agents are usually administered multiple times per day, particularly in the early period following ophthalmic surgery. Continuing efforts in drug development aim to identify alternatives to ophthalmic corticosteroid use, due to their well-known local and systemic negative side effects.

Natural triterpenoids, such as oleanolic acid and ursolic acid, which are derived from plant extracts, have been used extensively in Asian medicine for their anti-inflammatory and anticancer properties (Reference 1. Liu, 1995). A series of semi-synthetic triterpenoids was prepared based on the structure of oleanolic acid, and tested to identify compounds optimized for their ability to inhibit the induction of nitric oxide (NO) in primary mouse macrophages treated with interferon-gamma (IFN•; Reference 2. Honda, 1998).

RTA 408 is a novel oleanane triterpenoid within this class of compounds. The results from *in vitro* and *in vivo* preclinical studies conducted to date demonstrate that RTA 408, as well as other semi-synthetic triterpenoids, are potent activators of the Nrf2 (nuclear factor erythroid-derived 2) pathway and inhibitors of the NF- κ B (nuclear factor kappalight-chain-enhancer of activated B-cells) pathway, and thus induce an antioxidant and anti-inflammatory phenotype.

Reata has demonstrated in preclinical models that topical ocular administration of RTA 408 increases the expression of NQO1 (a prototypical Nrf2 target gene) in the corneal epithelium and the corneal endothelium of rabbits, with the greatest effect observed in the 1% dose group. Topical ocular administration of RTA 408 (2x/day), at concentrations as low as 0.01%, is efficacious *in vivo* as an anti-inflammatory agent in a rabbit model of paracentesis-induced ocular inflammation.

RTA 408 is readily absorbed and distributed into ocular tissues after topical ocular administration, with sustained concentrations observed for at least 24 hours after the last dose. This ocular pharmacokinetic profile is consistent with the efficacy observed with twice daily ocular dosing in rabbits.

Ocular GLP toxicity studies have been completed with RTA 408 Ophthalmic Suspension in rabbits and monkeys with repeated (4x/day) administration of RTA 408 (0.1%, 0.3%, and 1%) for 28 days. As expected, systemic exposure to RTA 408 was very low in rabbits and monkeys, with maximum concentrations (C_{max}) on Day 28 of approximately 3.0 and 2.6 ng/mL, respectively. Overall, the topical ocular administration of RTA 408 Ophthalmic Suspension, at concentrations of 0.1%, 0.3%, and 1% four times daily for 28 days in rabbits, but not monkeys, produced ocular irritation, but did not cause any ocular or systemic toxicity in rabbits or monkeys. Thus, the no-observed-adverse-effectlevel (NOAEL) was determined to be at least 1% RTA 408 Ophthalmic Suspension administered 4x/day for 28 days in rabbits and monkeys. The conjunctival irritation observed in the rabbit ocular GLP toxicity study was reversible, was not observed in a non-GLP study in rabbits, was not observed in the monkey ocular GLP toxicity study, and is readily monitorable in the clinic.

Although it is highly unlikely that meaningful systemic exposure will result following topical ocular administration in humans, the systemic toxicity potential of RTA 408 has been extensively investigated in rats and monkeys, with daily oral administration for up to 6 months in rats and 9 months in monkeys.

Based on an integrated assessment of the nonclinical data, it is concluded that RTA 408 has an acceptable safety profile for topical ophthalmic use as indicated in the proposed topical ocular study in patients following uncomplicated cataract surgery at concentrations of 0.5% and 1.0% with a BID dosage regimen.

2 STUDY OBJECTIVES

To evaluate the clinical efficacy and safety of RTA 408 Ophthalmic Suspension in two concentrations versus placebo in the treatment of patients with inflammation and pain following uncomplicated cataract surgery.

3 CLINICAL HYPOTHESES

It is hypothesized that RTA 408 Ophthalmic Suspension will be more effective than placebo in the alleviation of inflammation and pain following cataract surgery.

4 OVERALL STUDY DESIGN

This trial will be a multi-center, double-masked, randomized, dose-ranging, placebocontrolled study consisting of 6 visits over approximately 7 weeks (49 days). Randomization will be used to avoid bias in the assignment of patients to treatment, to increase the likelihood that known and unknown patient attributes (e.g., demographics and baseline characteristics) are evenly balanced across treatment groups, and to enhance the validity of statistical comparisons across treatment groups. Masked treatment will be used to reduce potential of bias during data collection and evaluation of clinical endpoints.

At Visit 1 (Day -1 to Day -28), patients will be screened to ensure that they meet all initial inclusion criteria and none of the exclusion criteria. Medical and medication histories will be taken, the patients will subjectively grade ocular pain using the scales provided, and pin-hole visual acuity will be assessed. The Investigator will then perform a slit lamp biomicroscopic examination with intraocular pressure (IOP) measurement, and grading of anterior chamber inflammation. A dilated indirect ophthalmoscopic examination will also be performed. Female patients of childbearing potential will be given a urine pregnancy test.

At Visit 2 (Day 1, 24 ± 6 hours post-surgery), patients' medical and medication histories will be updated, patients will be queried for ocular pain, pin-hole visual acuity will be assessed, and the Investigator will perform a slit lamp biomicroscopic evaluation, IOP

measurement, and grading of anterior chamber inflammation. Qualifying patients will then be randomized to one of the following treatment groups (in a 1:1:1 ratio): RTA 408 Ophthalmic Suspension 0.5% (N=35), RTA 408 Ophthalmic Suspension 1.0% (N=35), or placebo for RTA 408 Ophthalmic Suspension (N=35). Study drug will be dispensed along with the Study Drug Compliance Diary. A trained unmasked technician will instruct patients on how to instill the study drug twice daily in the morning and evening (approximately 12 hours apart) for 14 days on the eye that underwent surgery. The first dose of study drug will be instilled in-office.

At Visits 3 (Day 4 ± 1), 4 (Day 8 ± 1), and 5 (Day 15 ± 1), patients' medical and medication histories will be updated, patients will be queried for ocular pain, pin-hole visual acuity will be assessed, and the Investigator will perform a slit lamp biomicroscopic evaluation, IOP measurement, and grading of anterior chamber inflammation. AEs will be noted, and the Study Drug Compliance Diary will be reviewed. Day 14 will be the last day of study drug treatment at home. On Visit 5 (Day 15 ± 1), the study drug and Study Drug Compliance Diary will be collected.

At Visit 6 (Day 21 ± 1), patients' medical and medication histories will be updated, patients will be queried for ocular pain, pin-hole visual acuity will be assessed, and the Investigator will perform a slit lamp biomicroscopic evaluation, IOP assessment, and grading of anterior chamber inflammation. A dilated indirect ophthalmoscopic examination will also be performed. AEs will be noted, and a urine pregnancy test will be given to females of childbearing potential. Patients will then exit the study.

5 STUDY POPULATION

5.1 Number of Patients

Approximately 105 patients will be enrolled in this multi-center study, 35 per arm, in order to complete 31 patients per arm.

5.2 Study Population Characteristics

Patients age 18 and older who are scheduled to undergo ocular surgery, and who meet all inclusion criteria and none of the exclusion criteria.

5.3 Inclusion Criteria

Each patient must meet the following criteria:

- 1. Have provided written informed consent, approved by the appropriate institutional review board;
- 2. Be able to comply with study requirements and visit schedule;
- 3. Be greater than or equal to 18 years of age of either sex or any race;
- 4. Have undergone unilateral cataract extraction via phacoemulsification and posterior chamber intraocular lens (PCIOL) implantation in the study eye on the day prior to study enrollment/randomization;
- 5. Have a grade of ≥ 2 in anterior chamber cell score on day after surgery (Day 1) in the study eye;

- 6. Have a potential post-operative pin-hole visual acuity (VA) < 1.0 logarithm of the minimum angle of resolution (logMAR) in the operative eye and fellow eye as measured using an Early Treatment for Diabetic Retinopathy Study (ETDRS) chart;
- 7. (For females of childbearing potential) agree to have urine pregnancy testing performed at screening (must be negative) and at exit visit; must not be lactating; and must agree to use a medically acceptable form of birth control² throughout the study duration. Women of childbearing potential include all females who have experienced menarche and have not experienced menopause (as defined by amenorrhea for greater than 12 consecutive months) or have not undergone successful surgical sterilization (hysterectomy, bilateral tubal ligation, or bilateral oophorectomy).

5.4 Exclusion Criteria

Each patient may not meet any of the following:

- 1. Have any intraocular inflammation present in the study eye during the screening slit lamp examination;
- 2. Have a score greater than "0" on the Ocular Pain Assessment at Screening in the study eye;
- 3. Have an immunosuppressive disease or an autoimmune disease that in the opinion of the Investigator could affect the quality of the ocular surface;
- 4. Have active or chronic/recurrent ocular or systemic disease that is uncontrolled and will likely affect wound healing;
- 5. Currently have suspected or known malignancy or is currently receiving antineoplastic therapy;
- 6. Be a female who is currently pregnant, planning a pregnancy, lactating, not using a medically acceptable form of birth control throughout the study duration, or has a positive urine pregnancy test at screening;
- 7. Use anti-inflammatory agents, analgesics/pain relievers (including opioids, narcotics and other pain medications) or immunomodulating agents systemically, or in the study eye, and/or use medications for benign prostatic hyperplasia (BPH), from the washout period through the duration of the study. Washout periods for medications prior to surgery are as follows:
 - a. Medications for BPH (tamsulosin, silodosin, alfuzosin, finasteride): 28 days
 - b. Systemic corticosteroids: 14 days
 - c. Systemic analgesics/pain relievers (e.g., gabapentin, pregabalin, NSAIDs and opioids): 14 days

Note: Use of acetaminophen (up to 4,000 mg/day) and 'baby' aspirin (up to 81 mg/day) during the study are allowed. Use of an opioid during cataract surgery is allowed.

d. Periocular injection of any corticosteroid solution: 28 days

²Acceptable forms of birth control are spermicide with barrier, oral contraceptive, injectable or implantable method of contraception, transdermal contraceptive, intrauterine device, or surgical sterilization of partner. For non-sexually active females, abstinence will be considered an acceptable form of birth control.

- e. Corticosteroid depot in the study eye: 56 days after implantation
- f. Cyclosporine: 56 days
- g. Topical ocular corticosteroid: 7 days
- h. Topical ocular NSAID: 7 days
- 8. Have glaucoma or be taking medications to treat glaucoma in the study eye;
- 9. Have an intraocular pressure (IOP) ≤ 5 mmHg in either eye;
- 10. Currently have or have a history of Herpes Simplex Keratitis in the study eye;
- 11. Have active corneal abrasions or ulcers in the study eye;
- 12. Have active or a history of chronic or recurrent inflammatory eye disease (e.g. iritis, scleritis, uveitis, iridocyclitis, rubeosis iritis) in the study eye;
- 13. Have evidence of acute external ocular infections (bacterial, viral and/or fungal such as vaccinia, varicella, and other viral diseases of the cornea and conjunctiva); tuberculosis of the eye; corneal dystrophies; intraocular infections, dysthyroid ophthalmopathy, active chalazion, or uncontrolled blepharitis in the study eye;
- 14. Have uncontrolled and clinically significant dry eye syndrome in the study eye (artificial tears are allowed);
- 15. Have proliferative diabetic retinopathy (PDR), compromised macular function; significant macular diseases; clinically significant macular edema (CSME); or a history of cystoid macular edema in the study eye;
- 16. Have had corneal or retinal surgery (laser or incisional) within the past 6 months, or be planning to have laser or incisional surgery during the study period in the study eye (other than cataract surgery);
- 17. Have surgery planned or scheduled for the contralateral eye during the study;
- 18. Have previous ocular trauma with visible scarring or any deformities due to the trauma in the study eye;
- 19. Require the use of a contact lens or a collagen shield within 72 hours of investigational drug treatment or during the study period in the study eye; be unwilling to discontinue use of contact lenses during study period in the study eye;
- 20. Require use of non-diagnostic topical ophthalmic solutions (other than perioperative mydriatics, anesthetics and antiseptics, prophylactic antibiotics, lid scrubs for mild blepharitis, or artificial tears for the management of dry eye) in the study eye for the duration of the study;
- 21. Have known allergy or sensitivity to the investigational product or its components;
- 22. Have ocular hemorrhage in the study eye that interferes with evaluation of postsurgery inflammation;
- 23. Have undergone any other ophthalmic surgical procedure (e.g., vitrectomy, relaxing incisions, iridectomy, conjunctival excisions, use of iris hooks or other iris dilators, etc.) in addition to the cataract extraction procedure and PCIOL implantation in the study eye;
- 24. Have previously enrolled in this clinical study, or are planning to participate in another clinical trial during the follow-up period, that could confound the treatment or outcomes of this investigation;
- 25. Be excluded if the Investigator determines that the patient should not be included for reasons not already specified (e.g., systemic or other ocular

disease/abnormality), if the health of the patient or the validity of the study outcomes may be compromised by the patient's enrollment.

5.5 Withdrawal Criteria

If at any time during the study the investigator determines that a patient's safety has been compromised, the patient may be withdrawn from the study.

Patients may withdraw consent from the study at any time.

Sponsor and/or investigator may discontinue any patient for non-compliance or any valid medical reason (see Section 8.6.2).

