- Non-diagnostic topical ophthalmic solutions (other than perioperative mydriatics, anesthetics and antiseptics, prophylactic antibiotics, lid scrubs for mild blepharitis, or artificial tears for the management of dry eye) in the study eye
- Antineoplastic therapy
- Any other ophthalmic surgical procedure (e.g., vitrectomy, relaxing incisions, iridectomy, conjunctival excisions, use of iris hooks or other iris dilators, etc.) in addition to the cataract extraction procedure and PCIOL implantation in the study eye
- Plan to have laser or incisional surgery in the study eye (other than cataract surgery);
- Surgery planned or scheduled for the contralateral eye;

If a patient uses a disallowed medication, this use will be recorded as a protocol violation. Protocol violations must be reported to the IRB in accordance with their standard operating procedures.

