8.5 Compliance with Dosing

Site staff will review concomitant medication use at each visit.

Patients will be provided with a study drug compliance diary to document BID dosing for 14 days. Patient compliance with dosing will be assessed by in-office review of study drug compliance diary. Patients who miss more than 25% of their study drug doses (*more than* 7 total doses) will be considered non-compliant with dosing and a protocol deviation should be recorded.

8.6 **Patient Disposition**

8.6.1 Completed Patients

A completed patient is one who has not been discontinued from the study and continues study assessments through Visit 6 (Day 21).

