8.6.2 Discontinued Patients

Patients may be discontinued from the study prior to their completion of the study due to any of the following reasons:

- AEs
- Protocol violations
- Lack of efficacy
- Administrative reasons (e.g., inability to continue, lost to follow up)

- Sponsor termination of study
- Voluntary withdrawal
- Pregnancy:

If a female has a positive pregnancy test during the study, the patient should stop study treatment, and the Investigator will notify the sponsor immediately. The Investigator shall request copies of all related medical reports during the pregnancy and shall document the outcome of the pregnancy from the patient and/or patient's physician. The Investigator will retain these reports together with the patient's source documents and will provide a copy of all documentation to the sponsor.

• Other

Note: In addition, any patient may be discontinued for any sound medical reason.

Notification of a patient's discontinuation of study drug administration and the reason for discontinuation will be made to CRO and study Sponsor and will be clearly documented on the eCRF. Patients who receive escape medication are to discontinue study drug administration and are to remain in the study and be followed per the protocol to the end of the study. Patients who discontinue study drug administration for other reasons are encouraged to remain in the study and continue with study assessments through the end of the study.

Notification of a patient's discontinuation of study participation and the reason for discontinuation will be made to CRO and study Sponsor and will be clearly documented on the eCRF.

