9.1 Adverse Event

An AE is defined as any untoward medical occurrence associated with the use of a drug in humans, whether or not the event is considered drug-related. An AE can therefore be any unfavorable and unintended sign (e.g., an abnormal laboratory finding), symptom, or disease occurring after the first dose of study drug, without any judgment about causality. Any pre-existing medical condition that worsens after first administration of the study drug will also be considered a new AE. The AE reporting period ends upon study exit. Study drug includes the investigational drug under evaluation and placebo given during any stage of the study.

Documentation regarding the AE should be made as to the nature, date of onset, end date, severity, relationship to study drug, action(s) taken, seriousness, and outcome of any sign or symptom observed by the physician or reported by the patient upon indirect questioning.

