10.3 General Imputation Methods

The primary analyses of all efficacy data will use LOCF to impute missing data; data for visits after a patient is discontinued for lack of efficacy will be imputed as

failures for success/failure endpoints and will be imputed using LOCF for other endpoints. To check robustness of results, sensitivity analyses of the primary efficacy data will include analyses of observed data only, imputing data from patient visits after discontinuation for lack of efficacy as failures. Other imputation methods may be applied as additional sensitivity analyses.

Per Protocol analyses will use observed data only, with the exception of patients who have missing data due to discontinuation for lack of efficacy; for these patients, missing data after discontinuation will be imputed as failures.

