9.3 Safety

The Safety population includes all randomized patients who received at least one dose of investigational treatment. The Safety population will be analyzed as treated and will be used for the safety analyses. No data will be excluded for any reason.

10. Patient Disposition

Patient disposition will be presented in terms of the numbers and percentages of patients who were randomized. Patients who are not discontinued from the study will be considered study completers.

The total number of screened subjects with the number and percentage of screen failure subjects and reasons for screen failure will be displayed with the percentages calculated using total number of 13/FEB/2014 Confidential Page 12 of 21

Statistical Analysis Plan Protocol RTA 408-C-1307

Version 1.0

screen failures as the denominator. The number of patients in each of the populations (ITT, PP and Safety) will be displayed by treatment and percentages will be calculated using randomized patients as the denominator.

The number and percentage of patients with major protocol deviations will be summarized by treatment group for all randomized patients. The protocol deviations that will be summarized include: non-compliance with any scheduled study visit, non-compliance with study treatment, use of disallowed concomitant medications, non-compliance with study inclusion or exclusion criteria, non-compliance with study assessment procedures and other. A patient listing will be provided that includes the date of the deviation, the deviation description and the classification of whether the deviation was judged to be major or minor.

The number and percentage of patients prematurely discontinued from study treatment and the reasons for study treatment discontinuation will be summarized by treatment group for all randomized patients. The reasons for study treatment discontinuation that will be summarized include: adverse event (AE), protocol violation, lack of efficacy, administrative reasons, sponsor termination of study, voluntary withdrawal, pregnancy and other. A patient listing will be provided that includes the date of and reason for premature study treatment discontinuation.

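### Protocol 5.5 and 8.6.2 let a willing patient be removed from the study for non-compliance, protocol violations or AEs, so an obtainable Day 15 outcome can be replaced by LOCF

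*Protocol*

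**What the plan says.** Protocol 5.5 provides that "Sponsor and/or investigator may discontinue any patient for non-compliance or any valid medical reason", and points to 8.6.2. That section opens its list with "Patients may be discontinued from the study prior to their completion of the study due to any of the following reasons"; the list includes AEs, protocol violations, lack of efficacy, administrative reasons and an open category.

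Section 8.6.2 separates stopping study drug from leaving the study, with its own notification rule for each. Patients who receive escape medication must remain and be followed to the end. For everyone else the text is weaker: "Patients who discontinue study drug administration for other reasons are encouraged to remain in the study and continue with study assessments".

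Elsewhere the protocol asks only that such events be recorded. On prohibited medication (8.2.1): "If a patient uses a disallowed medication, this use will be recorded as a protocol violation". On missing more than 7 doses (8.5), the patient "will be considered non-compliant with dosing and a protocol deviation should be recorded".

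On missing outcomes, Protocol 10.3 says "The primary analyses of all efficacy data will use LOCF to impute missing data", and SAP 6.3 repeats this. The exception is visits after discontinuation for lack of efficacy, which count as failures. SAP 10 tabulates treatment discontinuation and study discontinuation separately, and both reason lists include adverse event and protocol violation.

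**The concern.** Non-compliance, protocol violations and AEs arise after randomisation and may depend on the treatment received. If they end follow-up, a patient who would have attended Visit 5 has no Day 15 cell grade, and a carried-forward value stands in for it in the first primary comparison. Inclusion criterion 5 requires a cell grade of at least 2 on Day 1, so no eye is a success at entry. A grade carried forward from an early visit will tend to be a failure even if the eye would have cleared.

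The direction of bias is not fixed. Removals from an active arm lower that arm's rate and work against the drug; an excess on placebo works in the drug's favour. Some safety information is also lost, because "The AE reporting period ends upon study exit". Protocol 9.5 still requires follow-up of unresolved AEs, so the loss is confined to new events after removal.

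**Working it through.** **Does the text permit removal from the study?** The 5.5 sentence does not itself say whether drug or study is meant. Its cross-reference settles this: the 8.6.2 list concerns the study, and that section treats stopping drug as a separate event. SAP 10 has the same separation and expects AEs and protocol violations among the reasons for leaving the study. The encouragement to remain applies to patients who stop drug and does not limit what the sponsor or investigator may do.

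**Which routes are realistic before Day 15?**
- Total doses: 2 × 14 = 28. The 8.5 threshold of more than 7 missed means at least 8.
- At nominal Day 4, 2 × 3 = 6 doses are due, or 7 with that morning's dose, so 8 missed is impossible.
- At Day 8, 2 × 7 = 14 are due, or 15 with that morning's dose. Eight missed is 8/15 = 53% to 8/14 = 57% of them.
- The dosing threshold will therefore rarely be met early. Section 5.5 does not tie non-compliance to that threshold, however, and the deviation categories in SAP 10 are wider: "non-compliance with any scheduled study visit, non-compliance with study treatment, use of disallowed concomitant medications", then eligibility and assessment procedures. The likelier early routes are disallowed medication, an eligibility violation found after randomisation, and AEs.

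**What happens to the outcome?** The patient stays in the ITT set, so the ITT definition is respected. Exits for lack of efficacy already count as failures and do not change the primary result. For the other exits before Visit 5, the Day 15 outcome is filled by LOCF.

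**How much is one outcome worth?** Inputs: 35 per arm (Protocol 4 and 5.1) and Pearson chi-squared at one-sided alpha 0.10 (Protocol 10.6, SAP 5), critical value 1.2816. One eye is 1/35 = 2.9 points. With x1 and x0 cleared eyes on active and placebo and p = (x1 + x0)/70,

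z = [(x1 − x0)/35] / √[p(1 − p) × 2/35], without continuity correction.

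| Placebo | Active | z | Significant? |
|---|---|---|---|
| 7/35 | 11/35 | 1.094 | no |
| 7/35 | 12/35 | 1.344 | yes |
| 8/35 | 13/35 | 1.304 | yes |
| 9/35 | 14/35 | 1.272 | no |
| 11/35 | 17/35 | 1.464 | yes |

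The smallest significant excess is 5 eyes for placebo counts of 4 to 8 and 6 eyes for counts of 9 to 21 (placebo rates 11% to 60%). One eye is 1/6 to 1/5, or 17% to 20%, of that excess.

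**Expected effect of a removal.** The documents give no clearance rates. Let q be the net chance that a removed, uncleared eye would have cleared by Day 15, assumed to be 10% to 50%. The expected fall in the arm's rate for k removals is kq/35.

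| | q = 10% | q = 50% |
|---|---|---|
| k = 1 | 0.3 points | 1.4 points |
| k = 2 | 0.6 points | 2.9 points |

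The allowance from 35 enrolled to 31 completers per arm covers losses of every cause through Visit 6. It does not estimate the number of removals by decision and is not used as one here.

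**The case against.** The strongest reply is that the protocol permits removal but never directs it. The 8.6.2 list can be read as a catalogue of disposition reasons: lack of efficacy is on it, yet escape patients must stay. The specific instructions for escape medication, unmasking, pregnancy, missed doses and disallowed medication either stop drug or only record the event. Patients who stop drug are encouraged to stay, an exit visit is sought (8.4.2), and reasons for leaving are tabulated by arm. Observed-data, multiple-imputation and missing-as-failure analyses are planned (SAP 6.3, Table 14.2.1.3). The routes are also narrow: a steroid given because study drug failed falls under the escape rule, and some AE exits would be safety withdrawals in any case.

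Much of this stands as a limit on weight. The effect is conditional, and on the assumed range one removal costs 0.1 to 0.5 of an eye, roughly 2% to 10% of the 5 to 6 needed. It does not remove the point. A discretion that serves no stated purpose remains, encouragement addressed to patients does not restrain it, and neither an exit visit nor a sensitivity analysis supplies the Day 15 grade.

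A further objection is that a Day 15 grade after disallowed anti-inflammatory use is confounded by that drug. The ITT definition already answers this: all data are included despite protocol violations, so keeping these patients needs no new analysis rule.

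**Conclusion.** The concern holds. Read together, 5.5 and 8.6.2 allow a willing patient to be taken out of the study for non-compliance, a protocol violation or an AE, and LOCF then replaces a Day 15 outcome that could have been measured. One eye that would have cleared is worth 2.9 points, about one fifth of the needed difference. The expected effect is 0.3 to 1.4 points for one removal and 0.6 to 2.9 for two, on the assumed 10% to 50% chance of later clearing. How many removals would occur, and in which arm, cannot be known from the documents, so no bias is demonstrated. The change is recommended because it is cheap and protects the first primary endpoint in a small trial; confidence in its practical weight is moderate.

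**What to change.** In Protocol 5.5 and 8.6.2:
- Make non-compliance, protocol violation, AE and lack of efficacy reasons to stop study drug only.
- State that these patients remain in the study and complete the remaining scheduled visits through Day 15 and Day 21 unless they withdraw consent. This extends the rule that 8.6.2 already applies to escape patients.
- Limit discontinuation from the study to withdrawn consent, loss to follow-up or inability to continue, safety or sound medical reasons that the investigator judges to preclude further assessment, and termination by the sponsor.
- Leave the pregnancy text, which already speaks of stopping treatment.

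Align the study-discontinuation reasons in SAP 10 and the eCRF pick-list.

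The cost is protocol and SAP wording, one pick-list, and a few already scheduled visits for patients who would otherwise have exited. The investigator's safety withdrawal is kept.
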